Hospital and clinic costs will be assessed from the health system perspective. For each ED visit and hospitalization in the MHHS, total hospital-specific costs will be obtained from the cost-accounting system for these hospitals. Costs for physician services provided at CMHH will be estimated using UTHealth claims data and Relative Value Units (RVUs) from the Medicare Fee Schedule. The costs at other hospitals outside MHHS will be estimated based on the mean costs of these encounters at MHHS. Costs for clinic visits at UT Health will be estimated using UTHealth claims data and using the standard RVU-based method. The costs for office visits occurring outside our center will be estimated based on the mean costs observed at UTHealth. For the social media intervention group, we will also add the costs of the personnel time spent curating and managing the educational material to be used in the social media platforms. The total time spent with the social media intervention will be prospectively collected by the PI (who will be primarily responsible for managing the social media intervention and will also include time from the pulmonologist [RM] and hospitalist [KS] whenever their input is required) and will then be multiplied by the unit time costs based on the personnel salary, fringes, and overhead costs. All costs will be inflated to the year of analysis based on the Consumer Price Index for medical services.

Data Analysis Plan:

Effect size, recruitment, power & statistical analysis

Based on retrospective data of patients hospitalized at CMHH as well as estimated national data,^{27,28} we estimate a 25% hospital readmission rate and 35% emergency visit rate within one year of discharge for those receiving usual asthma education. We also assume a 35% unplanned clinic visit rate within one year of discharge. Each admission accounts for 2.4 treatment days, and each clinic and ER visit accounts for 1 treatment day. In a population of 100 patients, we then expect the total number of treatment days to be 114 days or 1.14 days per child-year. With an expected 25% effect size (based on the 20%-30% effect size reported in the Cochrane reviews on the impact of asthma education on healthcare utilization among pediatric patients,⁴ recruitment of 200 patients will give 0.80 power to show reduction in total number of unplanned treatment days with probability of benefit >60%.

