Power analysis assumed data arise from negative binomial distribution with standard deviation 1.5 times mean total treatment days. In 1000 simulations, relative risks were estimated from negative binomial model with prior relative risks centered at 0 with credible interval 0.3-3.0 and posterior probabilities were derived from normal approximation of model coefficients.

We believe this to be a conservative estimate since we assume that each patient with readmission, clinic visit, and ER visit would only have done so once within the year. Previous studies suggest that there is a population of frequent healthcare utilizers, and that one visit often is the precursor for multiple subsequent visits in this population.²⁹⁻³¹ We also believe the 25% effect size is reasonable, as systematic reviews and previous studies have shown that asthma education can increase compliance with medications by at least 20%³², decrease hospital admissions by 20%, decrease ER utilization by 25%, and decrease clinic visits by more than 30%.⁴ We also believe the sample size is feasible. CMHH alone admits ~250 – 300 patients for asthma each year.

We propose the use of Bayesian analysis to provide direct estimates of the probability of benefit (reduction in treatment days and health system cost reduction) as well as the magnitude of benefit or harm. In this pilot study, some treatment effects that would be considered important for patients, families, and clinicians may not be statistically significant by traditional frequentist analysis. While we have planned feasible patient recruitment in this pilot study to demonstrate a high probability of benefit with moderate effect size, we have avoided arbitrary probability thresholds ($p < 0.05$) used in frequentist analysis to define trial success. Moreover, given the low-risk, low-cost nature of this intervention, substantial cost reduction could be achieved with small decreases in health care utilization. As the first pilot study testing efficacy of SME in the pediatric asthma population, our planned Bayesian analysis will allow study conclusions to depend on the probability of benefit based on actual observed effect size balanced with potential harms/costs from the intervention and will inform future implementation and expansion of the intervention to additional patient populations.

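### The printed usual-care inputs give 130 treatment days per 100 children (1.30 per child-year), not the stated 114 (1.14)

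*Combined protocol and SAP*

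**What the plan says.** All of this is in the Data Analysis Plan of the combined protocol and SAP, under effect size, recruitment, power and statistical analysis.

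- Event rates: "we estimate a 25% hospital readmission rate and 35% emergency visit rate within one year of discharge for those receiving usual asthma education", followed by "We also assume a 35% unplanned clinic visit rate within one year of discharge".
- Days per event: "Each admission accounts for 2.4 treatment days, and each clinic and ER visit accounts for 1 treatment day".
- Result, for 100 patients: "we then expect the total number of treatment days to be 114 days or 1.14 days per child-year".
- Power, after a 25% effect is introduced: "recruitment of 200 patients will give 0.80 power to show reduction in total number of unplanned treatment days with probability of benefit >60" per cent.
- Simulation: "Power analysis assumed data arise from negative binomial distribution with standard deviation 1.5 times mean total treatment days". The prior is described as follows: "In 1000 simulations, relative risks were estimated from negative binomial model with prior relative risks centered at 0 with credible interval 0.3-3.0".
- Repeat events: the estimate is called conservative because a patient with a readmission, clinic visit or ER visit "would only have done so once within the year".

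The Outcomes section defines treatment days as a plain sum over hospital, ED and clinic. The later paragraph on the analysis models centres the prior relative risk at 1, with the same 0.3 to 3.0 interval.

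**The concern.** The 114 is presented as following from the rates and days per event that precede it. Those inputs leave nothing open: three rates, three day counts and one event of each type per affected patient. A reader who multiplies and adds them does not get 114.

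This figure is the planning level of treatment days in the sample-size paragraph. It sets the absolute size of the 25% effect, and it is the estimate that the plan goes on to call conservative. If it cannot be derived, the reader does not know whether the total, one of the inputs or the label is wrong, or which mean was simulated.

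**Working it through.** **Inputs** (Data Analysis Plan, per 100 usual-care children): 25 readmissions at 2.4 days, 35 emergency visits at 1 day, 35 unplanned clinic visits at 1 day.

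**Attempt to reproduce 114**

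- Admission days: 25 × 2.4 = 60
- ED days: 35 × 1 = 35
- Clinic days: 35 × 1 = 35
- Total: 60 + 35 + 35 = **130**, or 1.30 per child-year

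The stated figure is not reproduced. The gap is 130 − 114 = 16 days, and 16/130 = 12%.

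**Effect of 25%**

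- From 130: 0.25 × 130 = 32.5 days per 100, leaving 97.5
- From 114: 0.25 × 114 = 28.5 days per 100, leaving 85.5

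**What could give 114**

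- Changing one input: (114 − 70)/25 = 1.76 days per admission; or (114 − 70)/2.4 = 18.3% readmission; or 114 − 60 − 35 = 19% for either ED or clinic. None of these is in the plan.
- Two-arm average: (130 + 97.5)/2 = 113.75.
- One ED day absorbed by every admission: 60 + (35 − 25) + 35 = 105.
- One ED day absorbed by 16 of the 25 admissions: 130 − 16 = 114.
- Removing an independent 25% overlap from both ED and clinic visits: 60 + 35 × 0.75 + 35 × 0.75 = 112.5.

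**Does it matter for power?** The check uses 100 per arm, relative risk 0.75 and a normal prior on the log relative risk centred at 0. Taking 0.3 to 3.0 as a 95% interval gives a prior SD of ln 3/1.96 = 0.56. The plan gives no level for this interval, so 95% is an assumption. The plan also does not say whether the SD of 1.5 times the mean applies within each arm or is one usual-care value for both.

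| SD reading | SE of log relative risk | Closed-form power for >60% |
|---|---|---|
| Each arm 1.5 × its own mean | √((2.25 + 2.25)/100) = 0.212 | 0.861 at either mean |
| Common dispersion | 0.219 at mean 1.14 | 0.851 (mean 1.14), 0.853 (mean 1.30) |
| One usual-care SD in both arms | √((2.25 + 2.25/0.75²)/100) = 0.250 | 0.809 at either mean |

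Negative binomial simulations with 2000 runs per case gave, at means 1.14 and 1.30, power of 0.872 and 0.870 (own-arm SD) and 0.825 and 0.815 (one usual-care SD). Power is therefore about 0.81 to 0.87, and the choice of mean hardly moves it.

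**Prior wording.** A relative risk of 0 lies outside the interval 0.3 to 3.0. On the log scale, 0 is a relative risk of 1, which is what the analysis-model paragraph states.

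**The case against.** The strongest reply is that 114 may be a correct number whose derivation was left out. The two-arm average rounds to 114, and a partial overlap of ED days with admissions reaches it exactly. Either could be the origin, so it cannot be said that 114 has no explanation. But the plan describes no overlap deduction. The rates are labelled as usual education, and the 25% effect is introduced only after 114 has been stated. If 114 is the average, the usual-care figure is still 130 and the sentence is mislabelled.

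A second reply is that neither 114 nor 130 is clearly the level of the primary outcome. The clinic input and the power sentence concern unplanned use, whereas the Outcomes section does not restrict treatment days to unplanned ones. This stands, and the figure is treated here only as the planning level in the sample-size paragraph.

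A third reply is that no decision depends on it. This also stands, and it limits the severity.

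A reader might infer more than the documents support:

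- **That the trial is wrongly sized.** Power is practically the same at 1.14 and 1.30.
- **That 0.80 is wrong.** It is compatible with the one-usual-care-SD reading (0.809 closed form, 0.815 to 0.825 simulated), given a Monte Carlo SE of √(0.8 × 0.2/1000) = 0.013 on the plan's 1000 runs. The other readings give 0.85 to 0.87. The description is too sparse to reject the figure, or to claim that it has been reproduced.
- **That the >60% target is itself an error.** It is an openly stated planning target, and the plan says that it avoids thresholds as a definition of trial success.
- **That the analysis prior is misplaced.** The analysis-model paragraph has it centred at 1, so the slip is in the wording.

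**Conclusion.** The point holds as an arithmetic inconsistency of minor severity. The printed inputs give 130 days per 100 children (1.30 per child-year). The stated 114 (1.14) is 16 days, or 12%, lower, and nothing in the plan connects the two. If 114 is read as usual care, the absolute reduction is understated by 32.5 − 28.5 = 4 days per 100 children.

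The 130 rests only on the plan's own rates, days per event and one-event-per-type rule. The statement that N and power are not materially affected rests on 100 per arm, relative risk 0.75, the SD tied to the mean, and 0.3 to 3.0 taken as a 95% interval.

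**What to change.** In the sample-size paragraph, do one of the following:

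- correct 114 and 1.14 to 130 and 1.30;
- correct whichever input is wrong;
- keep 114 and state that it is the average over both arms, or that it reflects an overlap deduction, with the deduction given.

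In every case, say which mean entered the simulation. In the same edit, write the simulation prior as relative risk centred at 1 (log relative risk 0), to match the analysis-model paragraph.

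The cost is one figure or one explanatory sentence, a statement of the simulated mean, and one phrase. No change to N and no new simulation is needed.

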3. Participants will have an informal avenue of communication to the team by tweeting questions or comments to the team.

Instagram

The research team will post photos and short videos to be shared with participants. Participants can comment on the posts to discuss or ask questions to the team.

Snapchat

The research team will post pictures and videos similar to the Instagram platform. The team will also create snapcodes that link participants to our cloud based asthma education website run via google drive. This will allow for text based education along with the typical photo based content of this platform.

Outcomes:

Primary Outcome: Total number of treatment days in a medical setting (hospital, ED, clinic) within one year of enrollment. Treatment days are defined as the summation of days in the hospital, ED, or in the clinic. We chose one year because of the chronicity of asthma, as well as its seasonal variation.

Secondary Outcomes: Total number of hospitalizations, total number of readmissions, total number of emergency room visits, and the total number of clinic visits, patient satisfaction and understanding of asthma education, number of missed days of school, and total estimated health system costs, hospital costs, and clinic costs.

Healthcare utilization will be primarily assessed by parental report. The PI will contact families every month and ask if their child had been admitted, visited the emergency room, had a clinic appointment for asthma, or missed any days of school within that month. We will also verify utilization of any of the 14 Memorial Hermann hospitals (MHHS) and the UT Health clinics from their respective electronic medical records and claims data. While we are aware of the risk of recall bias, we believe a contact every month is frequent enough to minimize the bias. We will also obtain multiple ways of contact (phone call, text, email, social media) in order to reduce loss to follow up.

Level of engagement will be tabulated by the following: Facebook engagement will be tracked through “likes,” comments, unfriending, completion of learning units, completion of polls. Twitter engagement will be tracked through “retweets,” comments, completion of polls, and unfollowings. Instagram engagement will be tracked by “likes,” comments, and unfollowings. Snapchat engagement will be tracked by number of snapcode links viewed, and any unfollowings.

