All statistical and economic analyses will be conducted under the intent-to-treat analyses principle using generalized linear models with appropriate link function based on data distribution (ie, negative binomial or Poisson with log link). All Bayesian models will use neutral, vaguely informative prior such as those with relative risk centered at 1 with credible interval range from 0.3-3.0 encompassing the largest likely effect size for major outcomes in RCTs. Cost differences between the two arms will be assessed using generalized linear models with log-link and gamma distribution. To account for patients who may not be hospitalized or incur hospital-related costs during the study period, zero-inflated models will be considered. All models will be adjusted for stratifying variables (asthma control, recruitment site, and age) and account for patient clustering as necessary. Optimal model fit for each outcome will be determined from model diagnostics and comparison of likelihood-based statistics. All analyses will be conducted in R.

Data Storage and Handling: We will use Research Electronic Data Capture (REDCap) to randomize patients and collect predefined study data needed to address each of our hypotheses. REDCap is a secure, web-based application designed to support data capture for research studies, providing: 1) an intuitive interface for validated data entry; 2) audit trails for tracking data manipulation and export procedures; 3) automated export procedures for seamless data downloads to common statistical packages; and 4) procedures for importing data from external sources

Study Procedures: Participants will be approached for enrolment during their index hospitalization. Consent will be obtained. Study duration will last one year from enrolment. Participants will be contacted once a month (12 contacts total) to assess healthcare utilization within that past month. The PI on enrollment will ask for several different methods of contact and ask which the participants prefer ie. calling - what times of day/day of week, emailing, texting, directly messaging on social media etc. The PI will contact each participant by their mode of preference once a month. During the follow up contacts, participants will also be asked a short questionnaire (approximately 10 minutes).

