Information to be gathered will be missed school days, total number of hospitalizations, emergency room visits, and clinic visits. We will also gather costs of these visits. Engagement data will be obtained from the various social media platforms.

Interpretation and Potential Importance of Findings:

If we are able to demonstrate successful effects of social media enhanced asthma education in decreasing unplanned healthcare utilization, we believe the impact to be substantial. First, there is a large disease burden. Asthma is the most common chronic disease in childhood that affects 5.5 million children in the United States. Second, the intervention is easily implementable since social media use is so ubiquitous. Third, the outcome of a cost dominant intervention has implications for tremendous savings on costs to the healthcare system. Compounding this, we think the results of the study would be easily generalizable – 1. To the adult population, encompassing another 19.2 million patients with asthma in the US (339 million worldwide), and 2. To other chronic pediatric medical conditions that have frequent unplanned healthcare utilization such as pediatric diabetes, sickle cell, and epilepsy.

Plans for Dissemination of Results:

Once the project is completed, we plan on dissemination of results through submissions to national conferences (Pediatric Academic Societies, American Academy Pediatrics, and Pediatric Hospital Medicine) as well as manuscript publication in a peer-reviewed journal (JAMA Pediatrics, Pediatrics, Hospital Pediatrics).

References

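### No utilization before enrollment is listed as a data item or covariate, which costs some precision and the planned means to show and adjust for chance imbalance in frequent utilizers

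*Combined protocol and SAP*

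**What the plan says.** The primary outcome (Outcomes) is a count over the year that follows enrollment: "Total number of treatment days in a medical setting (hospital, ED, clinic) within one year of enrollment". Study Procedures collects utilization forward in time only: "Participants will be contacted once a month (12 contacts total) to assess healthcare utilization within that past month". The list of data items that ends that section reads "Information to be gathered will be missed school days, total number of hospitalizations, emergency room visits, and clinic visits", plus costs and engagement, and names no period before enrollment.

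Study Procedures places the enrollment meeting in hospital: "Participants will be approached for enrolment during their index hospitalization". For the meeting itself, it describes one set of questions: "The PI on enrollment will ask for several different methods of contact and ask which the participants prefer". Population and the randomization section add what is needed for eligibility and stratification (other chronic conditions, internet and social media use, age). Prior utilization does not appear as an eligibility item, stratum, covariate or baseline descriptor.

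Two other statements bear on this. The power section says there are frequent utilizers and that "one visit often is the precursor for multiple subsequent visits in this population". Outcomes says of records "We will also verify utilization of any of the 14 Memorial Hermann hospitals (MHHS) and the UT Health clinics", using the electronic record and claims data.

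**The concern.** By the plan's own account, a child's earlier use predicts later use. Prior-year treatment days are therefore the natural baseline for this outcome, and the two sources needed (a bedside conversation and the health system's records) are already part of the trial.

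The outcome is a skewed count, so a small group of children carries much of it. In simulation from the plan's mean and standard deviation, the top 10% of children account for about 44% of all treatment days. Randomization is stratified by age only. With about 100 children per arm, frequent utilizers can fall unevenly by chance, and the plan includes no table that would show this and no model term that would adjust for it. The conclusions of this pilot are to rest on the observed effect size and the probability of benefit, so readers will want to know whether the arms started alike.

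**Working it through.** **Inputs from the plan.** 200 children at 1:1, so 100 per arm; control mean 1.14 days per child-year; 25% reduction (rate ratio 0.75); negative binomial with SD 1.5 times the mean; success if the posterior probability of benefit exceeds 60%; prior on the relative risk centered at 1 with interval 0.3 to 3.0. I take the prior as normal on the log scale with SD ln 3/1.96 = 0.561.

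**Assumed.** The documents give no year-to-year correlation. I use 0.4, 0.6 and 0.8 for the correlation of each child's log underlying rates in the two years.

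1. *The plan's power.* Dispersion k = 1.5² − 1/1.14 = 1.373. SE(log RR) = √[(1/1.14 + k + 1/0.855 + k)/100] = 0.219. With w = 0.561²/(0.561² + 0.219²) = 0.868, power = Φ(0.2877/0.219 − 0.2533/√0.868) = Φ(1.04) = 0.851. Simulation gives 0.849 to 0.856. The stated 0.80 is not reproduced and is on the low side. The stated 1.14 also does not follow from its components (25 × 2.4 + 35 + 35 = 130 days per 100 children, so 1.30), but using 1.30 moves power by only about 0.001. Neither discrepancy affects this point.

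2. *How much a baseline could explain.* If all overdispersion is stable between-child risk, the between-child share of the control-arm variance is 1.373/2.25 = 61%. But an admission brings 2.4 days at once. With the plan's event rates and stays of 2 or 3 days (assumed split 0.6/0.4, mean 2.4), the variance at a fixed rate is 0.25 × (0.6 × 4 + 0.4 × 9) + 0.70 = 2.20. The frailty variance is then 2.25 − 2.20/1.30² = 0.95, a share of 0.95/2.25 = 42%. The rest is clumping that prior use cannot predict.

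3. *Variance factor from adding log(1 + prior-year days).* Ranges are over repeated simulations of 500 to 2,000 trials each and differ by simulation error:

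| Correlation of log rates | Days Poisson given the child's rate | Admissions bring days in clumps |
|---|---|---|
| 0.4 | 1.01 to 1.05 | 1.00 to 1.02 |
| 0.6 | 1.06 to 1.14 | 1.02 to 1.06 |
| 0.8 | 1.20 to 1.24 | 1.08 to 1.10 |

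   As a cross-check, in the first model the correlation between log(1 + prior days) and follow-up days was 0.17, 0.27 and 0.37, and 1/(1 − r²) gives 1.03, 1.08 and 1.16.

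4. *In power.* Put SE = 0.219/√factor into step 1. Factor 1.00 gives 0.851, 1.05 gives 0.859, 1.11 gives 0.867 and 1.20 gives 0.879. The gain is about 0 to 3 points. In children, 200 × (factor − 1) is 0 at a factor of 1.00, 16 at 1.08 and 40 at 1.20.

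5. *How often imbalance arises.* If prior-year counts have the same SD-to-mean ratio, the SE of the log ratio of arm means is √(2 × 2.25/100) = 0.212. The chance of a ratio outside 0.80 to 1.25 is 2 × [1 − Φ(0.223/0.212)] = 29%; simulation gave 26 to 30%.

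6. *What it does to the estimate.* In the Poisson model with true rate ratio 0.75 and correlation 0.8, trials in which the SME arm starts heavier (ratio above 1.25) average 0.86 unadjusted and 0.76 adjusted. Those in which it starts lighter (below 0.80) average 0.64 and 0.72. At correlation 0.6 the pairs are 0.80 and 0.72, and 0.68 and 0.74. Clumped admissions would shrink these shifts.

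**The case against.** The strongest reply is that nothing is invalid here. Randomization makes the comparison unbiased, and the negative binomial dispersion carries the variation between heavy and light users into the posterior. The shifts in step 6 are ordinary sampling error. This stands, so the loss is one of precision and description.

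A second reply is that a reader might infer that imbalance in frequent utilizers could never be seen or corrected. The documents do not support that. Encounters in the Memorial Hermann and UT Health records will still be there at analysis, and a look-back could be pulled later. What a later look-back cannot supply is outside care and prior missed school days, which depend on asking parents. A covariate added after results are known is also less credible.

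A third reply is that the analysis section already names asthma control as an adjustment variable, and control could stand in for utilization risk. It is named there as a stratifying variable, but the randomization section stratifies by age only and no measurement of control is described. The other named factor, site, is constant in a single-site trial. As written, age is the only usable adjuster. If control is in fact measured at baseline, the added gain from prior utilization would be smaller than the figures above, which compare against a model with no covariates.

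Finally, silence is not proof. REDCap will hold predefined study data, and no data forms are included in the documents. The text shows that prior utilization is not listed. It does not show that nobody will ask. Likewise, the remark about frequent utilizers is made to defend the event-rate assumption and does not quantify how well earlier use predicts later use.

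**Conclusion.** The point holds as a cheap improvement to a valid design. The plan lists no pre-enrollment utilization as a data item or covariate, although it regards earlier visits as predictive and already has access to the sources. A reader might infer a biased comparison or a seriously underpowered trial; neither follows.

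The variance of the log rate ratio would fall by a factor of about 1.0 to 1.2, worth about 0 to 3 power points at the 60% threshold. This rests on an assumed correlation of 0.4 to 0.8 in underlying rates and on how much of the overdispersion is stable between-child risk. If multi-day admissions cause much of it, the lower end applies. The gain that does not depend on these assumptions is descriptive: a planned display of prior use by arm, with outside care and missed school days included.

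**What to change.** - Add a baseline assessment, completed before allocation is revealed, covering the 12 months before the index admission: asthma hospital days, ED visits, clinic visits and missed school days. Take it from parent report and the Memorial Hermann and UT Health records.
- Report these items by arm.
- Pre-specify log(1 + prior-year treatment days) as a covariate in the primary negative binomial model, with treatment days counted as in the outcome definition.
- If asthma control is meant to be a covariate, state how and when it is measured, and reconcile the list of stratifying variables with the randomization section.

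The cost is a few enrollment questions, a longer look-back in records already being opened, and one model term. Parents will recall outside care imperfectly. Because the answers precede allocation, that error lowers the gain but does not bias the comparison.
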